Potential genetic determinants of treatment response will be examined by the assessment of genetic variants in relation to treatment outcome. A blood sample will be obtained from patients who have signed a separate informed consent form for the pharmacogenomic analyses. The blood sample can be obtained at any visit post Screening, and the patient has agreed to be tested and has signed the separate informed consent form; i.e., the blood draw is not tied to any specific study visit, hence it can be obtained at any time post Screening. But due to circumstances caused by the COVID-19 pandemic and possibility of no further in-clinic visits after Baseline visit (Visit 2), it is strongly recommended that the pharmacogenomics blood sample be obtained at the Baseline visit (Visit 2).

The first step of the pharmacogenomic analyses will involve genotyping for allelic polymorphisms related to treatment response to TNX-102 SL. It is presumed that unused sample will be stored up to fifteen years, and potentially utilized to develop a pharmacogenomic test for predicting treatment response to TNX-102 SL.

Table 2: Study Design and Schedule of Assessments

Assessment	Screening and Washout Period ^a	Run-In Period (Diary for Symptoms)	Baseline/ Random- ization	Week 2 ^r	Week 6 ^r	Week 10 ^r	Week 14/ET ^b	Week 16/Post- Study Safety Follow Up ^S
Study Day	-35 to -1	-7 to -1	1	15 -4 /+7 days	43 ± 7 days	71 ± 7 days	99 -4 /+7 days	113 -4 /+ 7 days
Visit Number	1		2	3	4	5	6	7
Informed consent	X							
Inclusion/exclusion criteria	X							
Demographics	X							
Medical history	X		X ^k					
Prior/Concomitant medications	X		X ^k	X	X	X	X	X
Lifetime FM pharmacotherapy history	X							
Physical examination	X		X ^c				X	
Inspection of oral cavity ⁿ	X		X	X	X	X	X	
2016 Revision to 2010/2011 FM Diagnostic Criteria	X							
MINI 7.0.2 Modules A, C, I, J, K (MDE, Bipolar, EtOH, Substance Use, Psychotic Disorders)	X							
MSI-BPD	X							
Columbia-Suicide Severity Rating Scale (C-SSRS)	X		X	X	X	X	X	
Beck Depression Inventory (BDI-II) ^q	X		X	X	X	X	X	
In-clinic assessment of pain (24-hour & weekly recall) ^q	X ^p		X	X	X	X	X	
FIQR ^q			X	X	X	X	X	
PROMIS – Sleep Disturbance ^q			X	X	X	X	X	
PROMIS – Fatigue ^q			X	X	X	X	X	
PGIC Assessment ^q				X	X	X	X	

Assessment	Screening and Washout Period ^a	Run-In Period (Diary for Symptoms)	Baseline/ Random- ization	Week 2 ^r	Week 6 r	Week 10 ^r	Week 14/ET ^b	Week 16/Post- Study Safety Follow Up ⁸

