*/º The blood draw for the pharmacogenomic assessment can be obtained at any study visit post-Screening (including an Early Termination visit). Due to circumstances caused by the COVID-19 pandemic and possibility of no further in-clinic visits after Baseline visit (Visit 2), it is strongly recommended that the pharmacogenomics blood sample be obtained at the Baseline visit (Visit 2). It should only be obtained one time during the study. Separate written, signed informed consent is required if the patient is to participate in the optional pharmacogenomic assessment.

 p Weekly recall of daily average pain intensity on the NRS scale is required at the Screening Visit. Patients should only continue screening if they score ≥4 and ≤9.

^q For telephone visits, the patient will be mailed all the applicable patient reported outcomes for a given visit. The results of the BDI-II will be reviewed with the patient (specifically Question #9 which will allow further exploration of any suicidal thoughts or wishes implied by the patient's self-reported response, if applicable) during the phone call. C-SSRS interview should only be conducted after the BDI-II Question #9 inquiry, as any discrepancy between Question #9 response and C-SSRS suicidal ideation types endorsed for the same assessment period must be resolved to avoid presence of occult suicidal ideation not recognized by site staff.

^r Week 2, Week 6, and the Week 10 visits may be performed via telephone only when an in-clinic visit is not feasible due to the COVID-19 pandemic. Select safety assessments specifically required in-clinic will not be required for the telephone visits (e.g. vital signs and oral cavity exam). Telephone visits for Week 14/ET visits are to be strongly discouraged due to inability to obtain several safety measures (e.g. vital signs, physical exam, oral cavity exam, chemistry and hematology labs), but telephone visits will be permitted for Week 14/ET visit if attendance of an in-clinic visit is absolutely impossible or refused by the patient as a result of the COVID-19 pandemic and it is not feasible for the site to conduct a home visit. If a telephone Week 14/ET visit is performed, all efforts should be made to collect the missing assessments from that visit (e.g. vital signs, physical and oral cavity exam, chemistry and hematology labs) at an unscheduled follow up visit as soon as feasible.

⁸ Visit 7 (Week 16 or approximately 2 weeks after ET) will be a telephone visit.

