7. INVESTIGATIONAL PLAN

7.1. Overall Study Design

This is a Phase 3, randomized, parallel-group, double-blind, placebo-controlled, 16-week study designed to evaluate the efficacy and safety of TNX-102 SL 5.6 mg (2 x 2.8 mg tablets) taken daily at bedtime for the treatment of fibromyalgia. The study is to be conducted at approximately 30-40 investigational sites in the United States.

The study will consist of a Screening Visit (Visit 1, Days -35 to -8), a Baseline/Randomization Visit (Visit 2, Day 1), a Week 2 Visit (where the dose will be increased to 5.6 mg/day), and 3 more treatment visits (Weeks 6, 10 and 14 or Early Termination). The period between the Screening and Baseline Visit wills be at least 7 days, in order to allow for at least one week of daily pain data collection, and up to 35 days, to accommodate any necessary scheduling challenges or prohibited medication washout time. For extenuating circumstances, the duration of the Screening period may be increased to up to 49 days with Medical Monitor approval, and an option for a telephone visit will be available for Weeks 2, 6, and 10 for those unable to attend an in-clinic visit due to circumstances related to the COVID-19 pandemic. Additionally, a Week 14/ET telephone visit or home visit by site staff may be allowed on a case-by-case basis, approved by the Medical Monitor, if the only other choice is losing the patient completely from the study if patient absolutely cannot come in to the clinic for the visit. A safety follow up telephone visit will occur at Week 16. The total duration of the study, including Screening, will be approximately 17-21 weeks. The maximum treatment duration will be 14 weeks.

Eligible patients who provide written consent will have study assessments performed at Screening and will stop all excluded medications during the washout period, as required, through the Week 14 visit (Visit 6). An in-clinic 7-day recall NRS average daily pain intensity score at Screening must be ≥ 4 and ≤ 9 in order for the patient to remain eligible.

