11.1.4. Screening Assessments and Procedures

The following screening assessments/procedures will be completed in the following general order:

- Obtain written informed consent to participate
- Inclusion/exclusion criteria
- Demographics
- Medical history
- Confirmation that patient satisfies the 2016 Revisions to the 2010/2011 fibromyalgia diagnostic criteria (2010 American College of Rheumatology provisional diagnostic criteria/2011 self-report modification for survey and clinical research)
- Prior medication history
- Lifetime fibromyalgia pharmacotherapy history
- NRS assessment of 7-day recall of average daily pain. Patients should only continue screening if they score ≥ 4 and ≤ 9 .
- Mini International Psychiatric Interview 7.0.2 Modules A (Major Depressive Episode), C (Manic and Hypomanic Disorders), I (Alcohol Use Disorder), J (Substance Use Disorder), and K (Psychotic Disorders)
- MSI-BPD
- BDI-II. Any patient with a BDI-II total score > 24 or a response of 2 or 3 to item #9 (suicidal ideation) is not eligible for randomization.
- "Baseline/Screening" version of the C-SSRS. Any patient with C-SSRS Type 3, 4 or 5 ideation during the preceding 6 months or any suicidal behavior during the preceding 12 months should be screen failed.
 - a. Results of the C-SSRS and BDI-II should be reviewed together at each visit to ensure (1) the patient is not experiencing suicidal ideation or worsening depression that requires intervention and (2) both scales are providing a consistent clinical picture of the patient with regard to suicidality.
- Physical examination, including vital signs, height, weight and BMI. Patients with BMI>45 are not eligible.

- Thorough examination of the oral cavity. This examination should include a careful visual examination of the sublingual area, tongue, buccal mucosa, lips, palate and gums, aided with a tongue depressor, as well as palpation of the lips, hard palate, and floor of the mouth. Any abnormalities should be noted on the oral cavity examination source document.
- Clinical laboratory tests
- Drug screening
- Serum pregnancy test (for women of child-bearing potential) processed at central lab
- 12-lead electrocardiogram
- Only those patients meeting all of the inclusion and none of the exclusion criteria will be eligible to continue. Eligible patients will:
 - a. Be trained on diary completion, which will take into account how to accurately report their pain and provide information intended to mitigate placebo response.

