11.2.2. Baseline Visit

For patients who have qualified for randomization, these assessments and procedures will be completed in the following general order:

- Confirm patient's eligibility based on the diary data collected during the preceding 7 days
- Review completed diary data with the patient and have the patient complete training on how to accurately report pain and reduce placebo response.
- Update medical history (with any changes noted since screening)
- Assess changes in medication history and concomitant medications
- Have the patient complete the BDI-II. If the BDI score is >24, the patient is not eligible for randomization and should be screen failed. In addition, a score > 1 on item #9 (suicidal ideation) is exclusionary.
- Administer the "Since Last Visit" version of the C-SSRS. Any patient exhibiting Type 3, 4, or 5 suicidal ideation or any suicidal behavior since the Screening visit should be screen-failed and assessed for appropriate follow-up care.
 - a. Results of the C-SSRS and BDI-II should be reviewed together to ensure (1) the patient is not experiencing suicidal ideation or worsening depression that requires intervention and (2) both scales are providing a consistent clinical picture of the patient with regard to suicidality.
- Assess occurrence of adverse events
- Conduct a brief physical examination, including vital signs and weight
- Conduct a visual examination of the oral cavity. This examination should include a
 careful visual examination of the sublingual area, tongue, buccal mucosa, lips, palate
 and gums. Any abnormalities should be noted on the oral exam source document. It
 is recommended that both non-significant as well as significant findings be noted so
 that there is a complete and accurate baseline assessment available for comparison to
 findings at later visits.
- Perform urine pregnancy test (for women of child-bearing potential)
- Patient should complete the following patient-reported outcomes (PRO):
 - a. FIQR
 - b. Clinic administered assessment of pain by both 24-hour and weekly recall using 11-point (0-10) NRS scale

- c. PROMIS scales for sleep disturbance and fatigue
- d. CSFQ-14 female or male version, as appropriate
- Ensure that all PROs were accurately and fully completed
- Once it has been confirmed that the patient remains eligible, randomize patient via IRT Randomization System
- Dispense bottle of double-blind study drug as assigned via the IRT

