12.2.4. Clinic Assessment of Pain (24-hour and weekly recall)

In addition to the diary assessments of 24-hour pain recall (Section 12.2.1), patients will be asked to rate their average pain on paper using the 11-point (0-10) NRS scale at Visits 2, 3, 4, 5 and 6 using both a 24-hour and 7-day recall interval. There is no requirement to reconcile the pain responses obtained from these paper assessments to the 24-hour daily diary assessments.

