The CSFQ-14 is completed at baseline and Week 14/ET. It has a male and a female version, which will be analyzed separately. The CSFQ-14 will be analyzed for its total score, three subscales on phases of sexual response, and five subscales for dimensions of sexual functioning by using an Analysis of Covariance (ANCOVA) model. The model will include the fixed, categorical effects of treatment and pooled site, plus a baseline covariate corresponding to the subscale (or total) being analyzed. Significance testing will be based on least-squares means using a two-sided alpha=0.05 test and two-sided 95% confidence intervals will be presented. This outcome is considered to be supportive of the product's safety; other exploratory analyses are for further support of product efficacy.

[figure not shown]
Protocol: TNX-CY-F307 Page 29 of 45

Final v1.0

The FIQR exploratory endpoints and the in-clinic pain assessments will be analyzed using an MMRM including the fixed, categorical effects of treatment, pooled site, study week, and treatment by study week interaction, as well as the fixed covariates of baseline value and baseline value score-by-study week interaction. An unstructured covariance structure will be used to model the within-patient errors. If this analysis fails to converge, the following structures will be tested in this order: first order ante dependence, heterogeneous first order autoregressive, heterogeneous compound symmetry and compound symmetry with the first to give convergence used. The Kenward-Roger approximation will be used to estimate the denominator degrees of freedom. Note that the screening values will be used as baseline for the in-clinic pain outcomes.

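### SAP 10.3 takes screening values as baseline for both in-clinic pain outcomes, but only the weekly recall is clearly scheduled at screening, and SAP 8.1 and Protocol 13 point to Visit 2

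*SAP*

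**What the plan says.** SAP 10.3 lists in-clinic pain among the exploratory endpoints, with both a 24-hour and a weekly recall; SAP 3.2.2 defines each as a change from baseline. The analysis is an MMRM that includes the "fixed covariates of baseline value and baseline value score-by-study week interaction". The section then adds: "Note that the screening values will be used as baseline for the in-clinic pain outcomes". It gives no reason and does not distinguish the two recalls.

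SAP 8.1 sets the general rule: baseline is the last non-missing value before the first dose, with a separate seven-day average for diary scores. Protocol 13 likewise takes the value nearest to, but before, the first dose. SAP 13 lists one change from the planned analysis, the treatment of PGIC as a continuous variable.

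On data collection, the Visit 1 list in Protocol 11.1.4 contains "NRS assessment of 7-day recall of average daily pain" and no 24-hour item. Table 2 has a single row, labelled "In-clinic assessment of pain (24-hour & weekly recall", with an X at screening. The footnote on that X reads: "Weekly recall of daily average pain intensity on the NRS scale is required at the Screening Visit". Protocol 12.2.4 has the paper ratings made "at Visits 2, 3, 4, 5 and 6 using both a 24-hour and 7-day recall interval". The Visit 2 list in Protocol 11.2.2 includes "Clinic administered assessment of pain by both 24-hour and weekly recall using 11-point (0-10) NRS scale".

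**The concern.** The baseline sentence covers two outcomes, and the protocol clearly schedules a screening value for only one of them. If a programmer follows SAP 10.3, the 24-hour change from baseline cannot be formed from protocol-required data, and the baseline and baseline-by-week terms of its model have nothing to use. The diary's 24-hour score does not fill the gap: it is a separate electronic rating, and Protocol 12.2.4 says the paper and diary scores need not be reconciled.

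The weekly outcome can be computed, but from an early score. Within-arm changes would then mix change on treatment with whatever happened between screening and randomization, including washout in patients who need it. The screening weekly score is also an entry criterion (4 to 9), so some regression to the mean is to be expected. If that score predicts Week 14 less well than the Visit 2 score does, precision is lost as well.

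The stakes are limited. Both endpoints are exploratory, and SAP 8.1.1.1 treats p-values outside the sequential procedure as descriptive. SAP 10.3 does, however, offer these analyses as further support for efficacy, so they should be computable and consistently defined. Settling the baseline before unblinding also avoids a later choice between two candidates.

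**Working it through.** The plan gives no figure to reproduce here. The main check sets the passages side by side.

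**1. What is collected before the first dose**

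| In-clinic score | Visit 1 (screening) | Visit 2 (Day 1) |
|---|---|---|
| Weekly recall | Scheduled (11.1.4; Table 2 footnote p) | Scheduled (11.2.2; 12.2.4) |
| 24-hour recall | Not in 11.1.4; footnote p names only weekly recall; Table 2 row label ambiguous | Scheduled (11.2.2; 12.2.4) |

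**2. Which visit meets each baseline definition**

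In Protocol 11.2.2 the patient-reported outcomes come before randomization and dispensing. By Protocol 7.1 the first dose is taken that evening. The Visit 2 scores are therefore the last scheduled values before dosing for both recalls, so SAP 8.1 and Protocol 13 both select Visit 2. SAP 10.3 selects Visit 1.

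**3. How old the screening score is**

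Protocol 7.1: "The period between the Screening and Baseline Visit wills be at least 7 days". The same section allows up to 35 days, and 49 with Medical Monitor approval. Washout is planned after consent at Visit 1, so in patients who need it the screening score precedes washout. Not every patient does (Protocol 11.1.2).

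**4. Possible precision loss for weekly recall**

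The documents give no correlations, so the following are assumptions: r1 (screening with Week 14) of 0.2 to 0.3, and r2 (Visit 2 with Week 14) of 0.4 to 0.5. For a single baseline covariate at one time point:

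- Residual variance ratio = (1 − r1²)/(1 − r2²)
- CI width ratio = square root of the variance ratio
- Equivalent sample loss = 1 − 1/ratio
- Effective N = 470/ratio (planned N from SAP 6)

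| r1 | r2 | Variance ratio | CI width | Sample loss | Effective N |
|---|---|---|---|---|---|
| 0.3 | 0.4 | 0.91/0.84 = 1.083 | +4.1% | 7.7% | 434 |
| 0.2 | 0.4 | 0.96/0.84 = 1.143 | +6.9% | 12.5% | 411 |
| 0.3 | 0.5 | 0.91/0.75 = 1.213 | +10.2% | 17.6% | 387 |
| 0.2 | 0.5 | 0.96/0.75 = 1.280 | +13.1% | 21.9% | 367 |
| equal | equal | 1.000 | 0% | 0% | 470 |

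This simplifies the planned MMRM, which also has site and baseline-by-week terms, and it takes all 470 patients as observed at Week 14.

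**The case against.** The case for leaving the text alone, or for treating this as a minor clarification, has four parts.

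- **Table 2 may schedule both recalls at screening.** Protocol 11 refers to Table 2 for the detailed schedule, and its row names both recalls with an X at Visit 1. Footnote p says weekly recall is required; it does not say the 24-hour recall is omitted. Protocol 12.2.4 leaves out Visit 1 altogether, including the weekly recall that is certainly taken there, so it says little about which scale is used at screening. That last point stands. The gap rests on the 11.1.4 list and on footnote p, which sits on the very X in question and names only weekly recall. The case report form would settle it, but it is not available.
- **A specific rule overrides a general one.** SAP 8.1 already makes an exception for diary scores, and Protocol 13.4.5 leaves exploratory detail to the SAP. This could defend a screening baseline for weekly recall, though without a stated reason or an entry in SAP 13. It cannot supply a 24-hour score that the Visit 1 list does not schedule.
- **The precision figures rest on assumption.** This is true. Apart from the equality case, every row presumes that Visit 2 predicts better. The documents support only a possible loss of unknown size, and the finding does not depend on the figures.
- **The endpoints are exploratory.** This is also true. It limits the consequence but does not make the rule workable.

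**Conclusion.** The point holds. SAP 10.3 conflicts with SAP 8.1 and Protocol 13. On the reading given by Protocol 11.1.4 and footnote p, 0 of about 470 patients have a scheduled screening 24-hour score to serve as baseline. That count depends on the reading, because the Table 2 row label is ambiguous. If both recalls were in fact captured at screening, the conflict would remain, since the later pre-dose Visit 2 scores are what the general definitions select.

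For weekly recall the rule is workable but inferior for describing within-arm change. Any loss of precision runs from zero to the 13% wider interval shown above, depending on correlations the documents do not give. Both candidate baselines precede randomization, so the treatment contrast is not biased. The effect is confined to two exploratory endpoints; the primary diary endpoint and the key secondary endpoints are untouched. The correction should be made, but it does not threaten the trial's main conclusions.

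**What to change.** Delete the sentence in SAP 10.3 so that SAP 8.1 applies. The Visit 2 (Day 1, pre-dose) 24-hour and weekly recall scores then become the baselines and covariates for their respective outcomes. If the Visit 2 weekly score is missing, the last-non-missing rule in SAP 8.1 already falls back to the screening weekly score, so no extra text is needed.

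If a screening baseline is intended for weekly recall, say so for that outcome only, give the reason, list it in SAP 13, and name Visit 2 as the baseline for the 24-hour recall.

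In Protocol Table 2, state that the screening X in the in-clinic pain row means weekly recall only, after checking this against the case report form.

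The cost is one SAP sentence and one table clarification. No new data are needed, and the change should be made before unblinding.

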10.3.1 Exploratory Analyses of Single-Nucleotide Polymorphism (SNP) Subgroups

The response to TNX-102 SL therapy will be analyzed in subgroups defined by genetic analysis. Blood samples were collected from patients in TNX-CY-F307 after obtaining patient's signed pharmacogenomic informed consent form and Institutional Review Board approval. Laboratory quality germline DNA sequencing from this subgroup will be used to determine the genotypes and group patients by genetically defined alleles for exploratory analyses of treatment response.

10.4 Analyses by Dose

Given that TNX-102 SL is generally well tolerated, it is unlikely that a large number of patients will have a dose reduction to one tablet and hence it is nearly certain that an insufficient number will have such a reduction so as to allow the multiple imputation algorithm to return stable results taking dose into account. If more than 10% of the patients in the active arm have a dose reduction at any point in the study, summary statistics on observed values for the primary and key secondary outcomes will be reported for placebo and each dose, with active treatment patients grouped by whether they had a PI-directed dose reduction at any time point, regardless of the dose they were on at a particular time point. Placebo patients that had a "dose reduction" will not be grouped separately.

10.5	Additional Subgroup A	analyses		
		1		

Protocol: TNX-CY-F307 Page 30 of 45

Final v1.0

Protocol: TNX-CY-F307 Page 31 of 45

Final v1.0

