followed by the Baseline/Randomization Visit (Visit 2, Day 1), 4 treatment visits at Weeks 2, 6, 10, and 14 (or Early Termination), and a Week 16 telephone follow-up visit. The total duration of the study, including Screening, will be approximately 17-21 weeks. The maximum treatment duration will be 14 weeks.

Eligible patients who provide written informed consent will have study assessments performed at Screening and will stop all excluded medications during the washout period through the Week 14 visit (Visit 6). Patients will record their average pain intensity for the previous 24 hours in the evening every day from Visit 1 through Visit 6 on an electronic diary system. After recording Baseline Diary scores for at least 7 days, patients will return to the investigative site for Baseline assessments and randomization (Day 1), where they will be randomly assigned to receive TNX-102 SL or matching placebo sublingual tablets in a 1:1 ratio.

Patients will take the study drug sublingually daily at bedtime, starting on the day that they are randomized (Day 1), for 14 weeks. For the first two weeks of treatment, patients will start on TNX-102 SL 2.8 mg (1 tablet) or placebo. Upon return to the site¹ for the Week 2 visit (Visit 3), all patients will have the dose increased to TNX-102 SL 5.6 mg (2 x 2.8 mg tablets) or two placebo tablets. Patients will return to the site¹ for assessment of efficacy and safety, as well as dose tolerability, at Weeks 6, 10, and 14 (or Early Termination). A safety follow-up telephone visit will occur at Week 16.

In scenarios in which TNX-102 SL 5.6 mg, or 2 placebo tablets, is considered intolerable due to adverse event(s) and would otherwise lead to study discontinuation, with Medical Monitor approval, the Investigator may lower the dose back to 1 tablet every night (TNX-102 SL 2.8 mg or one placebo tablet). Re-challenge with 2 tablets TNX-102 SL 2.8 mg (5.6 mg dose)/placebo may be attempted at a later date if/when it is deemed clinically warranted by the Investigator, or the patient may remain on the lower dose for the remainder of the study.

Patients who wish to withdraw from the study may do so at any time.

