8. GENERAL ISSUES FOR STATISTICAL ANALYSIS

8.1 General Statistical Methodology

Descriptive summaries will be provided where appropriate for each of the primary and secondary variables. In general, tables will summarize data by treatment group and visit. All patients for a population in each treatment group will be grouped together; patients that reduce dose from two tablets per day to one tablet per day will be not be reported separately for the analyses described in this SAP, unless otherwise noted. If there are more than 10% of patients in the active arm with a dose reduction at any point in the study, summary statistics on key outcomes may be reported for patients with dose reductions.

Baseline characteristic and safety tables will be completed for the Safety Population unless otherwise specified. Efficacy tables will be presented for the ITT Population.

Continuous, quantitative variable summaries will include the number of patients (N) with non-missing values, mean, standard deviation, median, minimum, and maximum.

Categorical, qualitative variable summaries will include the frequency and percentage of patients who are in the particular category. In general, the denominator for the percentage calculation will be based upon the total number of patients in the study population for the treatment group unless otherwise specified.

Baseline values are defined as the last non-missing measurement prior to the first dose of study drug. For scores obtained via diary, baseline will be defined as the average of the scores from the 7 days prior to the baseline visit. Change from baseline will be defined as the post-baseline visit value minus the baseline value.

Study day is defined as assessment date – first dose date +1 for dates on/after first dose date and assessment date – first dose date for those before.

All analyses will be performed using SAS® Software version 9.4 or later.

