9. STUDY PATIENTS AND DEMOGRAPHICS

9.1 Disposition of Patients and Withdrawals

The numbers and percentage of patients screened, randomized, completing the study, and withdrawing from the study, along with reasons for withdrawal, will be tabulated overall and by treatment group. The number and percentage of patients in each analysis population will be reported. Additionally, the number and percentage of patients that have an investigator-directed dose reduction from two tablets per day to one tablet per day will be summarized. The disposition and withdrawal summaries will be based on all patients who have data entered into the database.

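### If triggered, the SAP 10.4 by-dose table splits only the active arm, and by reduction history, so its rows are not doses and can show a dose difference that is only selection

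*SAP*

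**What the plan says.** SAP 10.4 sets a trigger: "If more than 10% of the patients in the active arm have a dose reduction at any point in the study". When it is met, "summary statistics on observed values for the primary and key secondary outcomes will be reported for placebo and each dose". The next clause defines those groups: "with active treatment patients grouped by whether they had a PI-directed dose reduction at any time point, regardless of the dose they were on". Placebo patients who stepped down to one tablet "will not be grouped separately".

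SAP 8.1 has the same 10% trigger but makes the output optional ("summary statistics on key outcomes may be reported for patients with dose reductions") and does not confine it to active patients.

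The reduction rule is the same in both arms. The protocol synopsis (Methodology) and SAP 4.4 let the investigator, with Medical Monitor approval, go from two tablets of either product back to one when the patient would otherwise leave the study because of poor tolerability. Reduction need not be permanent: "Re-challenge with 2 tablets TNX-102 SL 2.8 mg (5.6 mg dose)/placebo may be attempted at a later date". Protocol 7.1 and SAP 4 put every patient on one tablet for Days 1 to 14.

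Reductions are identified in both arms. Protocol 10.2 requires them to be documented in the CRF, and SAP 9.1 plans a tabulation in which "the number and percentage of patients that have an investigator-directed dose reduction from two tablets per day to one tablet per day will be summarized".

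**The concern.** There are two separate faults.

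The first is the label. SAP 10.4 announces results by dose but files patients by whether they ever reduced. A reducer's visits on two tablets, before the reduction or after a re-challenge, count in the reduced group. In the first two weeks every active patient is on one tablet, so the never-reduced row is not a two-tablet row then either.

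The second is the comparison. A reduction happens after randomization and because of intolerance. Sorting the active arm by it, while leaving placebo reducers mixed in with all other placebo patients, sets groups selected on tolerability beside a group that is not. If patients who tolerate treatment poorly also fare differently on pain, that difference shows up in the rows as though dose had caused it.

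At stake is how a supporting table in the study report would be read. Nothing confirmatory depends on it.

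**Working it through.** **The plan's own figures.** 2 × 235 = 470 patients (SAP 6). Ten percent of 235 is 23.5, so the table appears when at least 24 active patients reduce.

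**Chance that the table appears** (binomial, 24 or more of 235), by assumed true reduction rate: 5%: 0.1%; 8%: 13%; 10%: 49%; 12%: 83%; 15%: 99%.

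**Bias when dose has no effect.** The scale is the SAP's (8.2.1): negative change is improvement.

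- Δ = true active-minus-placebo difference, the same at either dose. Assumed −0.5.
- g = mean change in reducers minus mean change in non-reducers, from causes other than dose; positive means less improvement. Not in the documents; run from −0.5 to 1.0, first taken as equal in both arms.
- r_p = share of placebo patients who reduce. Not in the documents; 4% and 12% assumed.

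The whole-placebo mean lies r_p × g above the mean of placebo non-reducers. Hence:

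- never-reduced active − all placebo = Δ − r_p × g
- ever-reduced active − all placebo = Δ + (1 − r_p) × g
- ever-reduced − never-reduced active = g, whatever r_p is

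| g | r_p | Never reduced vs placebo | Ever reduced vs placebo | Ever − never |
|---|---|---|---|---|
| −0.5 | 4% | −0.48 | −0.98 | −0.5 |
| 0 | 4% | −0.50 | −0.50 | 0 |
| 0.5 | 4% | −0.52 | −0.02 | 0.5 |
| 0.5 | 12% | −0.56 | −0.06 | 0.5 |
| 1.0 | 4% | −0.54 | +0.46 | 1.0 |
| 1.0 | 12% | −0.62 | +0.38 | 1.0 |

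Example (g = 1.0, r_p = 12%): −0.5 − 0.12 = −0.62, and −0.5 + 0.88 = +0.38. A simulation with an assumed SD of 2.0 agrees to within 0.01.

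**Would filing by current dose help?** Assume 12% of active patients reduce and 40% of those are back on two tablets by Week 14. The two-tablet group is then 0.88 + 0.12 × 0.40 = 0.928 of the arm, and 0.048 / 0.928 = 5.2% of it are reducers. The gap becomes (1 − 0.052) × g = 0.95g, which is 0.47 at g = 0.5 and 0.95 at g = 1.0. About 95% of the artefact remains, because current dose is also set by intolerance after randomization.

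**Would splitting placebo help?** Let g_a and g_p be the gaps in the active and placebo arms. Never-reduced active against never-reduced placebo gives Δ. Ever-reduced against ever-reduced gives Δ + g_a − g_p. The error disappears only if g_a = g_p; with g_a = 1.0 and g_p = 0.5, for example, 0.5 remains.

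**Precision.** With 24 reducers and 211 non-reducers, the 95% half-width of the difference between the active rows is 1.96 × SD × √(1/24 + 1/211): 0.76, 0.84 and 1.06 NRS points for assumed SDs of 1.8, 2.0 and 2.5.

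**The case against.** The table may never be produced. SAP 10.4 itself thinks many reductions unlikely, and Protocol 10.2 expects few. If it is produced, it holds summary statistics without a test or a stated active-placebo contrast. The trial's objectives concern 5.6 mg only, and the primary analysis compares the arms as randomized. The grouping rule is disclosed in the same sentence as the reference to doses, and with no table shell the row labels are an inference. At Week 14 most reductions will already have happened, so visits before a reduction matter little there. The difference between 8.1 and 10.4 is one between a general and a specific section. All of this stands, and it keeps the point small.

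A reader might also infer more than the documents support:

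- *That the table will flatter the full dose.* The sign and size of g are unknown; at zero nothing happens, and a negative g favors the reduced group.
- *That these are the only planned efficacy results by dose.* The content of SAP 10.5 on additional subgroups is not visible, so this cannot be established.
- *That filing by history instead of current dose causes the bias.* It causes the mislabeling. The selection is nearly the same under either filing.

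The objections do not answer the two remaining facts: the plan calls the groups doses when they are not, and it sorts one arm only, by an event identified in both.

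**Conclusion.** The concern holds as a minor point on a conditional, descriptive table. Followed as written, SAP 10.4 would present reduction histories as doses and set a tolerance-sorted active arm beside an unsorted placebo arm. With no true dose effect, the two active rows would still differ by g: 0.5 to 1.0 NRS points for g in that range, nothing at g = 0, and the reverse order at g = −0.5. These are illustrations on assumed values of g, r_p and Δ, not predictions. With about 24 reducers, chance alone could produce a gap of similar size. The primary analysis, the key secondary tests and type I error control are unaffected.

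**What to change.** In SAP 10.4:

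1. Label the groups *ever reduced* and *never reduced*, not as doses.
2. Apply the same split to placebo and show it beside the whole placebo arm.
3. State that the groups are formed after randomization and support no dose-response inference.
4. Make SAP 8.1 and 10.4 agree on whether the output is optional or required, and on which patients it covers.

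Filing visits by current dose should not be offered as an alternative, since it leaves nearly all of the selection in place.

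The cost is one SAP paragraph and the added placebo columns; no new data are needed. There are two downsides. The placebo reducer group may be small: at an assumed 4% it would be about 9 of 235 patients. The split also reduces the selection without removing it, because intolerance on placebo and on drug may pick out different patients.
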